11.2.3. Demography

- Age: Age at the reference activity, computed as the number of years between the date of birth and the reference activity. Note that due to incomplete date, the derived age may be incorrect by 1 year when month is missing from the birthdate. This may lead to an apparent inconsistency between the derived age and the eligibility criteria/the age category used for randomization.
- Conversion of weight to kg
The following conversion rule is used:
 - $\text{Weight in Kilogrammes} = \text{weight in Pounds} / 2.2 + \text{weight in Ounces} / 35.2$
The result is rounded to 2 decimals.
- Conversion of height to cm
The following conversion rule is used:
 - $\text{Height in Centimetres} = \text{Height in Feet} * 30.48 + \text{Height in Inches} * 2.54$
The result is rounded to the unit (ie no decimal).
- Conversion of temperature to °C
The following conversion rule is used:
 - $\text{Temperature in } ^\circ\text{Celsius} = ((\text{Temperature in } ^\circ\text{Fahrenheit} - 32) * 5) / 9$
The result is rounded to 1 decimal.

11.2.4. Immunogenicity

- For a given subject and given immunogenicity measurement, missing or non-evaluatable measurements will not be replaced. Therefore, an analysis will exclude subjects with missing or non-evaluatable measurements.
- The Geometric Mean Concentrations (GMCs) calculations are performed by taking the anti-log of the mean of the log titre transformations. Antibody concentrations below the cut-off of the assay will be given an arbitrary value of half the cut-off of the assay for the purpose of GMC calculation. The cut-off value is defined by the laboratory before the analysis.
- The percentage of subjects seropositive/seroprotected and associated two-sided 95% Clopper-Pearson confidence intervals (CIs) will be computed by vaccine group for each available immunogenicity monitoring.
- A subject seropositive for anti-CS antibody will be a subject whose antibody concentration will be greater than or equal to the cut-off value (anti-CS \geq 1.9 EU/ml).
- Seroprotection rate for anti-HBs antibody is defined as the percentage of subjects with antibody concentration greater than or equal to an established cut-off (anti-HBs \geq 10 mIU/ml).

11.2.5. Safety

- Handling of missing data: subjects who missed reporting symptoms (unsolicited or concomitant medications) will be treated as subjects without symptoms (unsolicited or concomitant medications, respectively). In case of significant non-compliance of study procedures for reporting symptoms, the analysis plan will be reassessed to ensure more accurate reporting of study data by further analysis.
- For the analysis of solicited symptoms, missing or non-evaluable measurements will not be replaced. Therefore the analysis of the solicited symptoms based on the ES will include only subjects/doses with documented safety data (i.e. symptom screen/sheet completed).
- For a given subject and the analysis of solicited symptoms within 7 days post-vaccination, missing or non-evaluable measurements will not be replaced. Therefore the analysis of the solicited symptoms based on the ES will include only vaccinated subjects for doses with documented safety data (i.e., symptom screen completed). More specifically the following rules will be used:
 - Subjects who documented the absence of a solicited symptom after one dose will be considered not having that symptom after that dose.
 - Subjects who documented the presence of a solicited symptom and fully or partially recorded daily measurement over the solicited period will be included in the summaries at that dose and classified according to their maximum observed daily recording over the solicited period.
 - Subjects who documented the presence of a solicited symptom after one dose without having recorded any daily measurement will be assigned to the lowest intensity category at that dose (i.e., 37.5°C for fever or grade 1 for other symptoms).
 - Doses without symptom sheets documented will be excluded.
- For analysis of unsolicited AEs, such as SAEs or AEs by primary MedDRA term, and for the analysis of concomitant medications, all vaccinated subjects will be considered.
- For the analysis, temperatures will be coded as follows:

Grade	Temperature
0	< 37.5°C (< 99.5°F)
1	≥ 37.5°C (≥ 99.5°F) to ≤ 38.0°C (100.4°F)
2	> 38.0°C (> 100.4°F) to ≤ 39.0°C (102.1°F)
3	> 39.0°C (102.1°F)

- For the analysis, local injection site redness and swelling will be coded as follows:

Grade	Temperature
0	0 mm
1	> 0 to ≤ 50 mm
2	> 50 mm to ≤ 100 mm
3	> 100 mm

Note that for all tables described in this section, the way the percentage of subjects will be derived will depend on the event analysed (see table below for details). As a result, the N value will differ from one table to another.

Event	N used for deriving % per subject for Vaccination phase	N used for deriving % per dose for Vaccination phase
Concomitant vaccination	All subjects with study vaccine administered	All study visits with study vaccine administered
Solicited general symptom	All subjects with at least one solicited general symptom documented as either present or absent (i.e., symptom screen completed)	All study visits with study vaccine administered and with at least one solicited general symptom documented as either present or absent (i.e., symptom screen completed)
Solicited local symptom	All subjects with at least one solicited local symptom documented as either present or absent (i.e., symptom screen completed)	All study visits with study vaccine administered and with at least one solicited local symptom documented as either present or absent (i.e., symptom screen completed)
Unsolicited symptom	All subjects with study vaccine administered	All study visits with study vaccine administered
Concomitant medication	All subjects with study vaccine administered	All study visits with study vaccine administered

- Related dose: The related dose for an event (e.g., AE, medication, vaccination,...) is the study dose given before an event. In case the event takes place on a day a study dose is given, if the investigator has indicated the timing (before or after the vaccination) the related dose for this event is the most recent study dose given before this event. If the investigator has not indicated the timing, the related dose will be that of the study dose even if the event actually took place before.

Number of decimals displayed:

The following decimal description from the decision rules will be used for demography, efficacy, immunogenicity and safety/reactogenicity results.

Display Table	Parameters	Number of decimal digits
Demographic characteristics	Mean, median age	1
Demographic characteristics	SD (age)	1
Reactogenicity	Mean, Min, Q1, Median, Q3, Max for duration	1
All summaries	p-value	3

Percentages and their corresponding confidence limits will be displayed with:

- no decimals when there are fewer than 50 subjects in each tabulated group
- one decimal when there are at least 50 subjects in at least one tabulated group
 - Exceptions will be made for percentages that are not 0% or 100% but appear as 0% or 100% due to rounding. For these specific cases the number of decimals will be increased until the displayed value is no longer 0% or 100%. Examples are given in the following table.

n/N	Displayed percentage
10/45	22%
1/45	2%
10/55	18.2%
1/55	1.8%
1/300	0.3%
1/3000	0.03%
1/30000	0.003%
299/300	99.7%
2999/3000	99.97%
29999/30000	99.997%

- The display of additional decimals for values close to 0% or 100% will be applied only to point estimates and not confidence limits, which can be rounded and displayed as 0% or 100%.
- Values of exactly 0% or 100% will be presented with no decimals regardless of the number of subjects per tabulated group.

Differences in percentages

Differences in percentages and their corresponding confidence limits will be displayed with one more decimal than the maximum number used to display the individual percentages, for example the difference between two percentages displayed with one decimal will be displayed with two decimals.

Serological summary statistics

The number of decimals used when displaying geometric mean titers (GMT) or concentrations (GMC) and their confidence limits is shown in the following table:

GMT or GMC value	Number of decimals to display
<0.1	3
>=0.1 and <10	2
>=10 and <1000	1
>=1000	0

When multiple categories of GMT or GMC values are present in the same table, the number of decimals displayed should match that of the smallest category (i.e. the one with the higher number of decimals). For example, if GMT or GMC values of <0.1 appear in the same table as values of >=0.1 and <10, 3 decimals should be displayed for both.

12. ANNEX 2: TABLES, FIGURES AND LISTINGS**12.1. Demographics & baseline characteristics**

Template #	Table Title	Output destination	Template name
Template 1	Summary of subject disposition from Enrolled Set to Randomized/Intent-To-Treat Set (Enrolled set)	Post-text	TCONSORT1PART1/Specific
Template 2	Summary of subject disposition from Intent-To-Treat Set to Per Protocol Set for analysis of immunogenicity and efficacy (Intent-to-treat set)	Post-text / in-text	TCONSORT1PART3
Template 3	Summary of visit attendance (Intent-to treat set)	Post-text	TMH1SOCPT
Template 3	Summary of visit attendance (Per protocol set for analysis of immunogenicity and efficacy for efficacy)	Post-text	TMH1SOCPT
Template 4	Summary of study completion with reasons for withdrawal (Intent-to-treat set)	Post-text / Web disclosure	TSL1WITHDRAWAL
Template 4	Summary of study completion with reasons for withdrawal (Per protocol set for analysis of immunogenicity and efficacy for efficacy)	Post-text	TSL1WITHDRAWAL
Template 5	Summary of important protocol deviations leading to elimination (Intent-to-treat set)	In-text / Post-text	TDV1PROTDEV
Template 6	Deviations from protocol for age and intervals between study visits (Intent-to-treat set)	Post-text	TDEVINT1INTVAL
Template 6	Deviations from protocol for age and intervals between study visits (Per protocol set for analysis of immunogenicity and efficacy for efficacy)	Post-text	TDEVINT1INTVAL
Template 10	Exposure to study vaccine (Intent-to-treat set)	In-text / Post-text	TEXOVW1EXPOBYBYVAC
Template 7	Summary of demographic characteristics and baseline characteristics (Intent-to-treat set)	In-text / Post-text	TSL1DEMOG
Template 7	Summary of demographic and baseline characteristics (Per protocol set for analysis of immunogenicity and efficacy for efficacy)	Post-text / in-text/Synopsis	TSL1DEMOG
Template 7	Summary of demographic and baseline characteristics by protection status (Per protocol set for analysis of immunogenicity and efficacy for efficacy)	Post-text	TSL1DEMOG
Template 8	Summary of demographic characteristics and baseline characteristics (Enrolled set)	Web posting	TSL1DEMOG
Template 9	Summary of previous Hepatitis B vaccination (Intent-to-treat set)	Post-text	Specific
Template 9	Summary of previous Hepatitis B vaccination (Per protocol set for analysis of immunogenicity and efficacy for efficacy)	Post-text	Specific
Template 32	Minimum and maximum visit dates (intent-to-treat)	Annex	TACTIV1DATE

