11.6. Derived and transformed data

- Immunogenicity
 - A subject seropositive for anti-CS antibody will be a subject whose antibody concentration will be greater than or equal to the cut-off value (anti-CS \geq 0.5 EU/ml).
 - Seroprotection rate for anti-HBs antibody is defined as the percentage of subjects with antibody concentration greater than or equal to an established cut-off (anti-HBs \geq 10 mIU/ml).
 - The geometric mean concentrations (GMC) calculations will be performed by taking the anti-log of the mean of the log transformations (base 10). Antibody concentrations below the cut-off of the assay will be given an arbitrary value of half the cut-off for the purpose of GMC calculation.
 - Handling of missing data: for a given subject and a given immunogenicity measurement, missing or non-evaluable measurements will not be replaced. Therefore, an analysis will exclude subjects with missing or non-evaluable measurements.
- Reactogenicity and safety
 - Handling of missing data: subjects who missed reporting symptoms (solicited/unsolicited or concomitant medications) will be treated as subjects without symptoms (solicited/unsolicited or concomitant medications, respectively). In case of significant non-compliance of study procedures for reporting symptoms, the analysis plan will be reassessed to ensure more accurate reporting of study data by further analysis.

- For the analysis of solicited symptom, missing or non-evaluable measurements will not be replaced. Therefore the analysis of the solicited symptoms based on the TVC will include only subjects/doses with documented safety data (i.e. symptom screen/sheet completed).

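### Solicited symptoms with no recorded severity are scored at the lowest grade: state this as an exception and show the range it leaves for the Grade 3 rate

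*SAP*

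**What the plan says.** SAP section 11.2.5 opens its handling of solicited symptoms with a general statement: "For the analysis of solicited symptoms, missing or non-evaluable measurements will not be replaced". The next bullet repeats it for the 7-day window: "analysis of solicited symptoms within 7 days post-vaccination, missing or non-evaluable measurements will not be replaced". Specific rules follow:

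- A symptom reported with some or all daily values is "classified according to their maximum observed daily recording over the solicited period".
- A subject who reports a symptom "without having recorded any daily measurement will be assigned to the lowest intensity category at that dose", which the SAP spells out as Grade 1, or 37.5°C for fever.
- For a missing sheet: "Doses without symptom sheets documented will be excluded".

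The denominator table in the same section keeps the ungraded subject in. For general symptoms it is "All subjects with at least one solicited general symptom documented as either present or absent (i.e., symptom screen completed"), with parallel wording for local symptoms.

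Protocol section 11.6 states the general principle, "For the analysis of solicited symptom, missing or non-evaluable measurements will not be replaced", and has no lowest-grade rule. Its preceding bullet, however, counts subjects who failed to report symptoms, solicited ones included, as symptom-free. The SAP drops the word solicited from that bullet. SAP section 9, on changes from planned analyses, mentions neither difference.

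SAP section 6.5.1 tabulates Grade 3 percentages for each solicited symptom. Template 21 has rows for any, related, Grade 3, Grade 3 related and medically attended visit. It has no row for unknown grade.

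**The concern.** A symptom known to have occurred but with no recorded severity could have been of any grade. Scoring it at the mildest grade is a best-case imputation on a safety read-out. It sits under a statement that nothing is replaced, so a reader of the report could take every Grade 1 entry, and every entry in the lowest fever row, as observed.

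Reactogenicity by schedule is a secondary safety objective. The protocol's rationale says the pediatric formulation has never been used in adults, and group 2PedFx receives 1.0 ml at its first two vaccinations. With 26 subjects per vaccine group, single records are visible in the percentages. SAP section 12.4 sends the Template 21 tables to web disclosure.

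**Working it through.** The documents give no figure to reproduce, so the check concerns the direction of the error and its largest possible size.

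**Inputs from the documents**
- N = 26 subjects per vaccine group (protocol section 5.1).
- An ungraded symptom is set to Grade 1 or 37.5°C (SAP section 11.2.5).
- Grade 3 fever is above 39.0°C (SAP sections 6.5.1 and 11.2.5), so an assigned 37.5°C can never be Grade 3.
- The subject stays in the denominator (SAP section 11.2.5).

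**Notation, for one symptom at one dose**
- g = subjects with an observed Grade 3.
- m = subjects with the symptom reported but no daily value. The documents do not give m; 1 to 3 per group is assumed for illustration.
- u = those of the m who were truly Grade 3, with 0 ≤ u ≤ m.

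**Formulas**
- Reported under the SAP rule: g/N.
- True rate, counting only this source of error: (g + u)/N.
- Error: g/N − (g + u)/N = −u/N. It is zero when u = 0 and negative otherwise. Enumeration over N = 5 to 26 and all feasible g, m and u found no positive value.
- Largest error per affected record: 1/26 = 3.8 percentage points.
- Upper bound, all unknowns counted as Grade 3: (g + m)/N.

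**Illustration with N = 26**

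| Observed Grade 3 (g) | SAP rule g/N | Upper bound, m = 1 | Upper bound, m = 2 | Upper bound, m = 3 |
|---|---|---|---|---|
| 0 | 0/26 = 0% | 1/26 = 3.8% | 2/26 = 7.7% | 3/26 = 11.5% |
| 2 | 2/26 = 7.7% | 3/26 = 11.5% | 4/26 = 15.4% | 5/26 = 19.2% |
| 4 | 4/26 = 15.4% | 5/26 = 19.2% | 6/26 = 23.1% | 7/26 = 26.9% |

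For scale, the exact 95% interval around 2/26 is already 0.9% to 25.1%.

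**Any-grade rate.** The symptom is counted as present whatever grade is assigned, so this rate does not change.

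**Differences between groups.** Take two groups, each with 2/26 observed. One hidden Grade 3 in the first makes the true difference, first minus second, 3/26 − 2/26 = +3.8 points. One in the second makes it −3.8 points. The report shows 0 in both cases, so the error in a comparison has no fixed sign.

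**Dropping the unknowns instead.** With g = 2 and m = 2 this gives 2/24 = 8.3%. The truth is 2/26 = 7.7% if u = 0 (8.3% is too high) and 4/26 = 15.4% if u = 2 (8.3% is too low). Removal from the denominator is therefore not a neutral alternative.

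**The case against.** The strongest reply has four parts.

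**The text can be read coherently.** The non-replacement statement is followed by its consequence, that only doses with a completed symptom screen are analysed, and then by specific rules, of which the lowest-grade assignment is one. The rule is explicit, pre-specified and programmable. This stands as far as it goes, and it is why the rule should not be called wrong as written. But entering 37.5°C where no temperature was recorded is literally a replacement, and missing sheets have their own rule, so the wording still needs reconciling.

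**The trigger is narrow and policed.** It needs a symptom marked present and no value on any of seven days. Diary cards are verified with the subject and unreturned cards pursued (protocol section 6.6.18). Omissions found in eCRF review can be sent back for clarification or correction (section 12.1). Compliance is tabulated (SAP Template 19) and solicited events are listed individually (SAP section 12.5). This stands: the number of such records is probably small.

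**The fever value adds nothing false to the lowest row.** Fever is defined as at least 37.5°C by the oral route, the route used for diary temperatures, so a documented fever belongs in the ≥37.5°C row. Only the higher rows can be understated. A reader might infer that these records should leave the temperature table; that would discard a known fever.

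**The stakes are limited.** Safety is a secondary objective, SAP section 7 makes all analyses descriptive, and no test or threshold depends on the Grade 3 rate. This also stands, and it limits the point to reporting.

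**Conclusion.** The point holds as a cheap improvement. For a symptom reported without any daily value, the SAP rule leaves a group's Grade 3 percentage correct or too low, by at most 3.8 percentage points per affected record at N = 26. The size depends on m and u, which the documents do not give; if no such record occurs, the effect is zero.

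Three stronger readings are tempting and are not supported:

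- **That reported Grade 3 reactogenicity as a whole can only be too low.** Only this rule's contribution has a fixed direction. Excluding doses without sheets can act either way, and so can comparisons between schedules.
- **That the SAP replaces a protocol rule that only forbids replacement.** Protocol section 11.6 also counts unreported solicited symptoms as absent, which is itself a favourable assumption and one the SAP removes. What can be said is that the protocol has no lowest-grade rule and SAP section 9 does not record its addition.
- **That the illustrative figures are expected effects.** Two ungraded records in one group, both truly Grade 3, would turn a true 4/26 = 15.4% into a reported 2/26 = 7.7%. That is the extreme case for m = 2, not a forecast.

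Primary efficacy is not affected.

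**What to change.** - In SAP section 11.2.5, state the lowest-grade assignment as an explicit exception to the non-replacement principle. List it in section 9 as a departure from protocol section 11.6, together with the deletion of solicited from the rule on unreported symptoms.
- Keep these records in the any-grade row of Template 21 and in the ≥37.5°C row of Template 22.
- Add a row for symptom present, grade unknown, to Templates 21 and 22. Template 29 already has an Unknown row for laboratory grades.
- Add one line giving the Grade 3 rate with unknowns counted as Grade 3, so that the report shows the range from g/N to (g + m)/N.
- Do not remove the records from the temperature table or from the Grade 3 denominator.

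The cost is SAP wording, one extra row and one extra line, with no new data. The upper bound for Grade 3 may look slightly less favourable. If there are no such records, the row shows zero and the two ends of the range coincide.

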12.2. Efficacy

Template #	Table / Figure Title	Output destination	Template name
Template 11	Parasitemia incidence defined by a positive blood slide and vaccine efficacy of each vaccination schedule versus Control group during challenge phase (Per protocol set for analysis of immunogenicity and efficacy)	Post-text / in-text / Web disclosure/Synopsis	Specific
Template 12	Time to onset of parasitemia in each vaccination schedule versus Control (by blood slide) (Per protocol set for analysis of immunogenicity and efficacy)	Post-text / Web disclosure	Specific
Template 12	Time to onset of parasitemia in each vaccination schedule versus AduFx (by blood slide) (Per protocol set for analysis of immunogenicity and efficacy)	Post-text/ Web disclosure	Specific
Template 13	Cumulative incidence of parasitemia onset defined by positive blood slide for all groups (Per protocol set for analysis of immunogenicity and efficacy)	Post-text	Specific
Template 11	Parasitemia incidence defined by a positive blood slide and vaccine efficacy of each vaccination schedule versus AduFx during challenge phase (Per protocol set for analysis of immunogenicity and efficacy)	Post-text/ Web disclosure	Specific

12.3. Immunogenicity

Template #	Table / Figure Title	Output destination	Template name
Anti-CS antibodies (repeat)			
Template 14	Number and percentage of subjects with anti-CS (repeat) equal or above 1.9 EU/mL and GMCs (Per protocol set for analysis of immunogenicity and efficacy)	Post-text / in-text / Web disclosure/Synopsis	TIS1GMT
Template 14	Number and percentage of subjects with anti-CS (repeat) equal or above 1.9 EU/mL and GMCs by protection status (Per protocol set for analysis of immunogenicity and efficacy)	Post-text	TIS1GMT
Template 15	Reverse cumulative distribution curve for anti-CS antibodies (repeat) post-vaccination (Per protocol set for analysis of immunogenicity and efficacy)	Post-text	FIS1REVCUM
Template 15	Reverse cumulative distribution curve for anti-CS antibodies (repeat) post-vaccination by protection status (Per protocol set for analysis of immunogenicity and efficacy)	Post-text	FIS1REVCUM
Template 15	Reverse cumulative distribution curve for anti-CS antibodies (repeat) at the time of the challenge (Per protocol set for analysis of immunogenicity and efficacy)	Post-text	FIS1REVCUM
Template 15	Reverse cumulative distribution curve for anti-CS antibodies (repeat) at the time of the challenge by protection status (Per protocol set for analysis of immunogenicity and efficacy)	Post-text	FIS1REVCUM
Template 17	Box and whiskers plot of anti-CS antibodies (repeat) at post-vaccination and the day of the challenge (Per protocol set for analysis of immunogenicity and efficacy)	Post-text	Specific
Template 17	Box and whiskers plot of anti-CS antibodies (repeat) at post-vaccination and the day of the challenge by protection status (Per protocol set for analysis of immunogenicity and efficacy)	Post-text	Specific

Template #	Table / Figure Title	Output destination	Template name
Template 18	Evolution over time for anti-CS antibodies (repeat) by group (Per protocol set for analysis of immunogenicity and efficacy)	Post-text	Specific
Template 18	Evolution over time for anti-CS antibodies (repeat) per protection status (Per protocol set for analysis of immunogenicity and efficacy)	Post-text	Specific
Template 16	Comparison of the log-transformed means of the anti-CS (repeat) antibodies at post-vaccination and at the time of the challenge of each vaccination schedule versus AduFx groups (Per protocol set for analysis of immunogenicity and efficacy)	Post-text	specific
Template 16	Comparison of the log-transformed means of the anti-CS (repeat) antibodies at post-vaccination and at the time of the challenge between Protected and Non-Protected groups (Per protocol set for analysis of immunogenicity and efficacy)	Post-text	specific
Anti-CS antibodies (full length)			
Template 14	Number and percentage of subjects with anti-CS (full length) equal or above 200 1/DIL and GMTs (Per protocol set for analysis of immunogenicity and efficacy)	Post-text	TIS1GMT
Template 14	Number and percentage of subjects with anti-CS (full length) equal or above 200 1/DIL and GMTs by protection status (Per protocol set for analysis of immunogenicity and efficacy)	Post-text	TIS1GMT
Template 15	Reverse cumulative distribution curve for anti-CS antibodies (full length) at post-vaccination (Per protocol set for analysis of immunogenicity and efficacy)	Post-text	FIS1REVCUM
Template 15	Reverse cumulative distribution curve for anti-CS antibodies (full length) at post-vaccination by protection status (Per protocol set for analysis of immunogenicity and efficacy)	Post-text	FIS1REVCUM
Template 15	Reverse cumulative distribution curve for anti-CS antibodies (full length) at the time of the challenge (Per protocol set for analysis of immunogenicity and efficacy)	Post-text	FIS1REVCUM
Template 15	Reverse cumulative distribution curve for anti-CS antibodies (full length) at the time of the challenge by protection status (Per protocol set for analysis of immunogenicity and efficacy)	Post-text	FIS1REVCUM
Template 17	Box and whiskers plot of anti-CS antibodies (full length) at post-vaccination and the day of the challenge (Per protocol set for analysis of immunogenicity and efficacy)	Post-text	Specific
Template 17	Box and whiskers plot of anti-CS antibodies at post-vaccination and the day of the challenge (full length) by protection status (Per protocol set for analysis of immunogenicity and efficacy)	Post-text	Specific
Template 18	Evolution over time for anti-CS antibodies (full length) by group (Per protocol set for analysis of immunogenicity and efficacy)	Post-text	Specific
Template 18	Evolution over time for anti-CS antibodies (full length) per protection status (Per protocol set for analysis of immunogenicity and efficacy)	Post-text	Specific
Template 16	Comparison of the log-transformed means of the anti-CS (full length) antibodies at post-vaccination and at the time of the challenge of each vaccination schedule versus AduFx	Post-text	specific

Template #	Table / Figure Title	Output destination	Template name
	groups (Per protocol set for analysis of immunogenicity and efficacy)		
Template 16	Comparison of the log-transformed means of the anti-CS antibodies (full length) at post-vaccination and at the time of the challenge between Protected and Non-Protected groups (Per protocol set for analysis of immunogenicity and efficacy)	Post-text	specific
Anti-CS antibodies (C-term)			
Template 14	Number and percentage of subjects with anti-CS (C-term) equal or above 100 EPT and GMTs (Per protocol set for analysis of immunogenicity and efficacy)	Post-text	TIS1GMT
Template 14	Number and percentage of subjects with anti-CS (C-term) equal or above 100 EPT and GMTs by protection status (Per protocol set for analysis of immunogenicity and efficacy)	Post-text	TIS1GMT
Template 15	Reverse cumulative distribution curve for anti-CS antibodies (C-term) at post-vaccination (Per protocol set for analysis of immunogenicity and efficacy)	Post-text	FIS1REVCUM
Template 15	Reverse cumulative distribution curve for anti-CS antibodies (C-term) at post-vaccination by protection status (Per protocol set for analysis of immunogenicity and efficacy)	Post-text	FIS1REVCUM
Template 15	Reverse cumulative distribution curve for anti-CS antibodies (C-term) at the time of the challenge (Per protocol set for analysis of immunogenicity and efficacy)	Post-text	FIS1REVCUM
Template 15	Reverse cumulative distribution curve for anti-CS antibodies (C-term) at the time of the challenge by protection status (Per protocol set for analysis of immunogenicity and efficacy)	Post-text	FIS1REVCUM
Template 17	Box and whiskers plot of anti-CS antibodies (C-term) at post-vaccination and the day of the challenge (Per protocol set for analysis of immunogenicity and efficacy)	Post-text	Specific
Template 17	Box and whiskers plot of anti-CS antibodies (C-term) at post-vaccination and the day of the challenge by protection status (Per protocol set for analysis of immunogenicity and efficacy)	Post-text	Specific
Template 18	Evolution over time for anti-CS antibodies (C-term) by group (Per protocol set for analysis of immunogenicity and efficacy)	Post-text	Specific
Template 18	Evolution over time for anti-CS antibodies (C-term) per protection status (Per protocol set for analysis of immunogenicity and efficacy)	Post-text	Specific
Template 16	Comparison of the log-transformed means of the anti-CS (C-term) antibodies at post-vaccination and at the time of the challenge of each vaccination schedule versus AduFx groups (Per protocol set for analysis of immunogenicity and efficacy)	Post-text	specific
Template 16	Comparison of the log-transformed means of the anti-CS antibodies (C-term) at post-vaccination and at the time of the challenge between Protected and Non-Protected groups (Per protocol set for analysis of immunogenicity and efficacy)	Post-text	specific

Template #	Table / Figure Title	Output destination	Template name
Anti-CS Avidity Index (repeat)			
Template 16	Comparison of the log-transformed means of the anti-CS avidity index (repeat) at post-vaccination and at the time of the challenge of each vaccination schedule versus AduFx groups (Per protocol set for analysis of immunogenicity and efficacy)	Post-text	Specific
Template 16	Comparison of the log-transformed means for anti-CS avidity index (repeat) at post-vaccination and at the time of the challenge on Protected and Non-Protected groups (Per protocol set for analysis of immunogenicity and efficacy)	Post-text	Specific
Template 17	Box and whiskers plot of anti-CS avidity index (repeat) at post-vaccination and at the time of the challenge (Per protocol set for analysis of immunogenicity and efficacy)	Post-text	Specific
Template 17	Box and whiskers plot of anti-CS avidity index (repeat) at post-vaccination and at the time of the challenge per protection status (Per protocol set for analysis of immunogenicity and efficacy)	Post-text	Specific
Anti-CS Avidity Index post dose (full length)			
Template 16	Comparison of the log-transformed means of the anti-CS avidity index (full length) at post-vaccination and at the time of the challenge of each vaccination schedule versus AduFx groups (Per protocol set for analysis of immunogenicity and efficacy)	Post-text	Specific
Template 16	Comparison of the log-transformed means for anti-CS avidity index (full length) at post-vaccination and at the time of the challenge on Protected and Non-Protected groups (Per protocol set for analysis of immunogenicity and efficacy)	Post-text	Specific
Template 17	Box and whiskers plot of anti-CS avidity index (full length) at post-vaccination and at the time of the challenge (Per protocol set for analysis of immunogenicity and efficacy)	Post-text	Specific
Template 17	Box and whiskers plot of anti-CS avidity index (full length) at post-vaccination and at the time of the challenge per protection status (Per protocol set for analysis of immunogenicity and efficacy)	Post-text	Specific
Anti-CS Avidity Index post dose (C-term)			
Template 16	Comparison of the log-transformed means of the anti-CS avidity index (C-term) at post-vaccination and at the time of the challenge of each vaccination schedule versus AduFx groups (Per protocol set for analysis of immunogenicity and efficacy)	Post-text	Specific
Template 16	Comparison of the log-transformed means for anti-CS avidity index (C-term) at post-vaccination and at the time of the challenge on Protected and Non-Protected groups (Per protocol set for analysis of immunogenicity and efficacy)	Post-text	Specific
Template 17	Box and whiskers plot of anti-CS avidity index (C-term) at post-vaccination and at the time of the challenge (Per protocol set for analysis of immunogenicity and efficacy)	Post-text	Specific
Template 17	Box and whiskers plot of anti-CS avidity index (C-term) at post-vaccination and at the time of the challenge per protection status (Per protocol set for analysis of immunogenicity and efficacy)	Post-text	Specific

Template #	Table / Figure Title	Output destination	Template name
Anti-HBs antibodies			
Template 14	Number and percentage of subjects with anti-HBs equal or above 6.2 and 10 mIU/ml and GMCs (Per protocol set for analysis of immunogenicity and efficacy)	Post-text / in-text / Web disclosure	TIS1GMT
Template 14	Number and percentage of subjects with anti-HBs equal or above 6.2 and 10 mIU/ml and GMCs by protection status (Per protocol set for analysis of immunogenicity and efficacy)	Post-text	TIS1GMT
Template 15	Reverse cumulative distribution curve for anti-HBs antibodies at post-vaccination (Per protocol set for analysis of immunogenicity and efficacy)	Post-text	FIS1REVCUM
Template 15	Reverse cumulative distribution curve for anti-HBs antibodies at the time of the challenge (Per protocol set for analysis of immunogenicity and efficacy)	Post-text	FIS1REVCUM
Template 15	Reverse cumulative distribution curve for anti-HBs antibodies at post-vaccination by protection status (Per protocol set for analysis of immunogenicity and efficacy)	Post-text	FIS1REVCUM
Template 15	Reverse cumulative distribution curve for anti-HBs antibodies at the time of the challenge by protection status (Per protocol set for analysis of immunogenicity and efficacy)	Post-text	FIS1REVCUM

